4.5.6 Treatment of Nivolumab-Related Infusion Reactions

Since nivolumab contains only human immunoglobulin protein sequences, it is unlikely to be immunogenic and induce infusion or hypersensitivity reactions. However, if such a reaction were to occur, it might manifest with fever, chills, rigors, headache, rash, pruritus, arthralgias, hypo- or hypertension, bronchospasm, or other symptoms. All Grade 3 or 4 infusion reactions should be reported within 24 hours to the BMS Medical Monitor and reported as an SAE if criteria are met. Infusion reactions should be graded according to NCI CTCAE (version 4.0) guidelines.

Treatment recommendations are provided below and may be modified based on local treatment standards and guidelines as appropriate:

For Grade 1 symptoms: (Mild reaction; infusion interruption not indicated; intervention not indicated)

Remain at bedside and monitor subject until recovery from symptoms. The following prophylactic premedications are recommended for future infusions: diphenhydramine 50 mg (or equivalent) and/or paracetamol 325 to 1000 mg (acetaminophen) at least 30 minutes before additional nivolumab administrations.

For Grade 2 symptoms: (Moderate reaction requires therapy or infusion interruption but responds promptly to symptomatic treatment [eg, antihistamines, non-steroidal anti-inflammatory drugs, narcotics, corticosteroids, bronchodilators, IV fluids]; prophylactic medications indicated for ≤ 24 hours).

Stop the nivolumab infusion, begin an IV infusion of normal saline, and treat the subject with diphenhydramine 50 mg IV (or equivalent) and/or paracetamol 325 to 1000 mg (acetaminophen); remain at bedside and monitor subject until resolution of symptoms. Corticosteroid or

bronchodilator therapy may also be administered as appropriate. If the infusion is interrupted, then restart the infusion at 50% of the original infusion rate when symptoms resolve; if no further complications ensue after 30 minutes, the rate may be increased to 100% of the original infusion rate. Monitor subject closely. If symptoms recur then no further nivolumab will be administered at that visit. Administer diphenhydramine 50 mg IV, and remain at bedside and monitor the subject until resolution of symptoms. The amount of study drug infused must be recorded on the electronic case report form (eCRF). The following prophylactic premedications are recommended for future infusions: diphenhydramine 50 mg (or equivalent) and/or paracetamol 325 to 1000 mg (acetaminophen) should be administered at least 30 minutes before additional nivolumab administrations. If necessary, corticosteroids (recommended dose: up to 25 mg of IV hydrocortisone or equivalent) may be used.

For Grade 3 or Grade 4 symptoms: (Severe reaction, Grade 3: prolonged [ie, not rapidly responsive to symptomatic medication and/or brief interruption of infusion]; recurrence of symptoms following initial improvement; hospitalization indicated for other clinical sequelae [eg, renal impairment, pulmonary infiltrates]). Grade 4: (life-threatening; pressor or ventilatory support indicated).

Immediately discontinue infusion of nivolumab. Begin an IV infusion of normal saline, and treat the subject as follows. Recommend bronchodilators, epinephrine 0.2 to 1 mg of a 1:1,000 solution for subcutaneous administration or 0.1 to 0.25 mg of a 1:10,000 solution injected slowly for IV administration, and/or diphenhydramine 50 mg IV with methylprednisolone 100 mg IV (or equivalent), as needed. Subject should be monitored until the investigator is comfortable that the symptoms will not recur. Nivolumab will be permanently discontinued. Investigators should follow their institutional guidelines for the treatment of anaphylaxis. Remain at bedside and monitor subject until recovery from symptoms.

In the case of late-occurring hypersensitivity symptoms (eg, appearance of a localized or generalized pruritus within 1 week after treatment), symptomatic treatment may be given (eg, oral antihistamine, or corticosteroids).

4.6 Blinding/Unblinding

The Sponsor, subjects, investigator and site staff will be blinded to the study therapy administered. Each investigative site must assign an unblinded pharmacist/designee, and an unblinded site monitor will be assigned to provide oversight of drug supply and other unblinded study documentation.

Blinding of treatment assignment is critical to the integrity of this clinical study. However, in the event of a medical emergency of pregnancy in an individual subject in which knowledge of the investigational product is critical to the subject's management, the blind for that subject may be broken by the investigator. The subject's safety takes priority over any other considerations in determining if the treatment assignment should be unblinded.

Before breaking the blind of an individual subject's treatment, the investigator should determine that the unblinded information is necessary, ie, that it will alter the subject's immediate management. In many cases, particularly when the emergency is clearly not related to the

investigational product, the problem may be properly managed by assuming that the subject is receiving active product. It is highly desirable that the decision to unblind treatment assignment be discussed with the Medical Monitor, but the investigator always has ultimate authority for the decision to unblind. The actual TASK of unblinding can be delegated by the investigator to a designee assigned the task on the Delegation of Authority. The Principal Investigator or appointed designee should only call in for emergency unblinding AFTER the decision to unblind the subject has been documented.

For this study, the method of unblinding for emergency purposes is through the IVRS. For information on how to unblind for emergency, please consult the IVRS manual.

In cases of accidental unblinding, contact the BMS Medical Monitor and ensure every attempt is made to preserve the blind.

Any request to unblind a subject for non-emergency purposes should be discussed with the BMS Medical Monitor.

Designated staff of BMS Research & Development may be unblinded prior to database lock to facilitate the bioanalytical analysis of pharmacokinetic samples and immunogenicity. A bioanalytical scientist in the Bioanalytical Sciences department of BMS Research & Development (or a designee in the external central bioanalytical laboratory) will be unblinded to the randomized treatment assignments in order to minimize unnecessary bioanalytical analysis of samples.

To further minimize bias, the investigative clinical site staff is blinded to results from PD-L1 analysis.

4.7 Treatment Compliance

Treatment compliance will be monitored by drug accountability as well as the subject's medical record and electronic CRF (eCRF).

4.8 Destruction of Study Drug

For this study, study drugs (those supplied by BMS or sourced by the investigator) such as partially used study drug containers, vials and syringes may be destroyed on site.

Any unused study drugs can only be destroyed after being inspected and reconciled by the responsible Study Monitor unless study drug containers must be immediately destroyed as required for safety, or to meet local regulations (eg, cytotoxics or biologics).

On-site destruction is allowed provided the following minimal standards are met:

- On-site disposal practices must not expose humans to risks from the drug.
- On-site disposal practices and procedures are in agreement with applicable laws and regulations, including any special requirements for controlled or hazardous substances.
- Written procedures for on-site disposal are available and followed. The procedures must be filed with the site's SOPs and a copy provided to BMS upon request.

- Records are maintained that allow for traceability of each container, including the date disposed of, quantity disposed, and identification of the person disposing the containers. The method of disposal, ie, incinerator, licensed sanitary landfill, or licensed waste disposal vendor must be documented.
- Accountability and disposal records are complete, up-to-date, and available for the Monitor to review throughout the clinical trial period.

If conditions for destruction cannot be met the responsible Study Monitor will make arrangements for return of study drug.

It is the investigator's responsibility to arrange for disposal of all empty containers, provided that procedures for proper disposal have been established according to applicable federal, state, local, and institutional guidelines and procedures, and provided that appropriate records of disposal are kept.

4.9 Return of Study Drug

If study drug will not be destroyed upon completion or termination of the study, all unused and/or partially used study drug that was supplied by BMS must be returned to BMS. The return of study drug will be arranged by the responsible Study Monitor.

It is the investigator's responsibility to arrange for disposal of all empty containers, provided that procedures for proper disposal have been established according to applicable federal, state, local, and institutional guidelines and procedures, and provided that appropriate records of disposal are kept.

5 STUDY ASSESSMENTS AND PROCEDURES

5.1 Flow Chart/Time and Events Schedule

Table 5.1-1: Screening Procedural Outline (CA209274)

Procedure	Screening Visit	Notes
Eligibility Assessments		
Informed Consent	X	IC in screening for protocol participation; Study allows for re-enrollment of a subject that has discontinued the study as a pre-randomization failure. If re-enrolled, the subject must be re-consented and assigned a new subject number from IVRS.
Inclusion/Exclusion Criteria	X	All inclusion/exclusion criteria should be assessed and confirmed prior to randomization.
Medical History	X	Including smoking history
Tumor Tissue Sample	X	Sufficient tumor tissue from the resected site of disease (a block or a minimum of 10 unstained slides) must be available and sent to a central laboratory for biomarker analysis. PD-L1 status will be assessed prior to randomization. See Section 5.6.1
Prior Cancer Therapy	X	All prior therapy should be reported.
██████████	X	██████████ ██████████
Safety Assessments		
Physical Examination	X	General physical examination including assessment for hearing loss and peripheral neuropathy as needed within 14 days prior to randomization
Vital Signs	X	Including BP, HR and temperature. Obtain vital signs at the screening visit and within 72 hours prior to first dose.
Physical Measurements	X	Section 5.3 . Include Height and weight. Within 14 days prior to randomization
Assessment of Signs and Symptoms	X	Within 14 days prior to randomization
Concomitant Medication Collection	X	Within 14 days prior to randomization

Table 5.1-1: Screening Procedural Outline (CA209274)

Procedure	Screening Visit	Notes
Laboratory Tests	X	
CBC w/differential and platelet count, Chemistry panel including: LDH, AST, ALT, ALP, T.Bili, BUN or serum urea level, creatinine, Ca, Mg, Na, K, Cl, Glucose within 14 days prior to randomization
 
Urinalysis/Urine Cytology as clinically indicated within 14 days prior to randomization.
 
Amylase, lipase, albumin, TSH (Reflex to Free T4, Free T3 for abnormal TSH result), Hepatitis B surface antigen (HBV sAg), and hepatitis C antibody (HCV Ab) or Hepatitis C RNA (HCV RNA) within 28 days prior to randomization

Pregnancy Test (WOCBP only)	X	Serum or urine to be done at screening visit and repeated within 24 hours prior to first dose of study therapy
Efficacy Assessment		
Baseline Tumor Imaging Assessment	X	
CT of chest, and CT or MRI of abdomen, pelvis, upper urinary tract and all known or suspected sites of disease (including cystoscopy in subjects with upper GU primaries who still have bladder intact) within 28 days prior to randomization.
 
MRI brain within 28 days prior to randomization for subjects with clinical suspicion or history of brain/leptomeningeal metastases.

IVRS		
Register Subject in IVRS	X	A call must be made to the IVRS to register subject after signing informed consent.

Table 5.1-2: Treatment Phase (for subjects receiving nivolumab/placebo)

Procedure	During Treatment On Day 1 of Every Cycle (Cycle = 2 weeks)	Notes
Safety Assessments		
Targeted Physical Examination	X	Targeted examination must include at a minimum the following body systems: Cardiovascular Gastrointestinal Pulmonary
Vital Signs	X	Including BP, HR and temperature. Obtain vital signs within 72 hours prior to each dose.
Physical Measurements (including performance status)	X	Weight and ECOG performance status. See Appendix 2 for ECOG Performance Status scale.
Review of Concomitant Medication	X	
Adverse Events Assessment	X	
Laboratory Tests	X	CBC w/differential and platelet count, Chemistry panel including: LDH, AST, ALT, ALP, T. Bili, BUN or serum urea level, creatinine, Ca ⁺⁺ , Mg ⁺⁺ , Na ⁺ , K ⁺ , Cl ⁻ , LDH, albumin, glucose, amylase, lipase. TSH (Reflex to Free T4, Free T3 for abnormal TSH result) to be performed every 6 weeks (every 3 cycles) Urine cytology as clinically indicated (eg, to confirm recurrence in the bladder) On-study local laboratory assessments should be done within 72 hours prior to each dose through Week 23 visit and every alternative dose thereafter. Liver function tests (AST, ALT, ALP, T. Bili) will be analyzed within 72 hours prior to each dose throughout the treatment period.
Pregnancy Test (WOCBP only)	X	Serum or urine pregnancy test to be done within 24 hours prior to first dose, and then every 4 weeks (+/- 1 week) regardless of dosing schedule, or more frequently/at a frequency per local regulations/requirements.

Table 5.1-2: Treatment Phase (for subjects receiving nivolumab/placebo)

Procedure	During Treatment On Day 1 of Every Cycle (Cycle = 2 weeks)	Notes
Efficacy Assessments		
Tumor Imaging Assessment	
 • Non-cystoscopy tumor imaging assessments will occur every 12 weeks from the date of first dose to Week 96 (ie, Week 12, 24, 36, 48, 60, 72, 84, 96; +/- 1 week), then every 16 weeks from Week 96 to Week 160 (ie, Week 112, 128, 144, 160; +/- 2 weeks), then every 24 weeks until non-urothelial tract recurrence or treatment is discontinued (whichever occurs later) for a maximum of 5 years (ie, Week 184, 208, 232, 256; +/- 4 weeks). • Non-cystoscopy tumor imaging assessments: CT of chest, and CT or MRI of abdomen, pelvis, upper urinary tract, and all known sites of disease. Use same imaging method as was used at screening/baseline. • Cystoscopy in subjects with upper GU primaries who still have bladder intact will occur in addition to other tumor imaging assessments every 12 weeks from the date of first dose to Week 48 (ie, Week 12, 24, 36, 48 +/- 1 week), then every 24 weeks from Week 48 to Week 96 (i.e. Week 72, 96; +/- 2 weeks), then every 48 weeks until non-urothelial tract recurrence or treatment is discontinued (whichever occurs later) for a maximum of 5 years (i.e. Week 96, 144, 192, 240; +/- 4 weeks). 	
[REDACTED]	[REDACTED]	
[REDACTED]	[REDACTED]	
[REDACTED]	[REDACTED]	[REDACTED]
[REDACTED]	[REDACTED]	
[REDACTED]	[REDACTED]	
[REDACTED]	[REDACTED]	
[REDACTED]	[REDACTED]	
[REDACTED]	[REDACTED]	
[REDACTED]	[REDACTED]	

Table 5.1-2: Treatment Phase (for subjects receiving nivolumab/placebo)

Procedure	During Treatment On Day 1 of Every Cycle (Cycle = 2 weeks)	Notes
████████████████████		████████████████████
█		████████████████████
██		
████████████████████		████████████████████
████████████████████		████████████████████
Clinical Drug Supplies		
Randomization	X	Call IVRS for randomization (Tumor tissue submitted to central lab must be logged as received and PD-L1 results must be documented by the central lab in IVRS prior to randomization. Allow approximately 10 business days from the date of shipping for tissue to be received and processed.)
IVRS Drug Vial Assignment	X	Vials may be assigned up to 3 days prior to first dose date.
Dispense Study Drug	X	Within 3 days from vial allocation, the subject must receive the first dose of study medication. Subjects may be dosed no less than 12 days between doses.

Table 5.1-3: Follow-Up Period Following Discontinuation from Study Therapy			
Procedure	Follow Up, Visits 1 and 2^a	Survival Follow-Up Visits^b	Notes
Safety Assessments			
Targeted Physical Examination	X		To assess for potential late emergent study drug related issues Targeted examination must include at a minimum the following body systems: Cardiovascular Gastrointestinal Pulmonary
Adverse Events Assessment	X		In Survival Follow-Up period only to include toxicities from study therapy. Immune-mediated adverse drug reactions will be followed until resolution.
Review of Subsequent Therapy	X	X	Subsequent Cancer Therapy
[REDACTED]	[REDACTED]		[REDACTED]
Pregnancy Test (WOCBP only)	X		Serum or urine

Table 5.1-3: Follow-Up Period Following Discontinuation from Study Therapy			
Procedure	Follow Up, Visits 1 and 2^a	Survival Follow-Up Visits^b	Notes
Efficacy Assessments			
Tumor Imaging Assessment	See note	See note	
Only for subjects who enter the follow-up period without non-urothelial tract recurrence.
 
 • Non-cystoscopy tumor imaging assessments will occur every 12 weeks from the date of first dose to Week 96 (ie, Week 12, 24, 36, 48, 60, 72, 84, 96; +/- 1 week), then every 16 weeks from Week 96 to Week 160 (i.e. Week 112, 128, 144, 160; +/- 2 weeks), then every 24 weeks until non-urothelial tract recurrence or treatment is discontinued (whichever occurs later) for a maximum of 5 years (ie, Week 184, 208, 232, 256; +/- 4 weeks). • Non-cystoscopy tumor imaging assessments: CT of chest, and CT or MRI of abdomen, pelvis, upper urinary tract, and all known sites of disease. Use same imaging method as was used at screening/baseline. • Cystoscopy in subjects with upper GU primaries who still have bladder intact will occur in addition to other tumor imaging assessments every 12 weeks from the date of first dose to Week 48 (i.e. Week 12, 24, 36, 48 +/- 1 week), then every 24 weeks from Week 48 to Week 96 (i.e. Week 72, 96; +/- 2 weeks), then every 48 weeks until non-urothelial tract recurrence or treatment is discontinued (whichever occurs later) for a maximum of 5 years (i.e. Week 96, 144, 192, 240; +/- 4 weeks).
[REDACTED]			
[REDACTED]	■		[REDACTED]
[REDACTED]	■	■	[REDACTED]
[REDACTED]	■		[REDACTED]
[REDACTED]			
[REDACTED]	■	■	[REDACTED]

Table 5.1-3: Follow-Up Period Following Discontinuation from Study Therapy			
Procedure	Follow Up, Visits 1 and 2^a	Survival Follow-Up Visits^b	Notes
[REDACTED]	■	■	[REDACTED]
[REDACTED]	■	■	[REDACTED]
[REDACTED]	■	■	[REDACTED]
[REDACTED]			
[REDACTED]	■		[REDACTED]
[REDACTED]	■		[REDACTED]
Subject Status			
Survival Status		X	Section 3.6. Collect every 3 months in Survival Visits until death, lost to follow-up, or withdrawal of study consent. May be performed by phone contact or office visit. Additionally, data regarding subsequent anti-cancer therapy will also be collected.

- a Subjects must be followed for at least 100 days after last dose of study therapy Follow-up visit #1 (FU1) occurs approximately 35 days (+/- 7 days) after the last dose or coinciding with the date of discontinuation (+/- 7 days) if date of discontinuation is greater than 35 days after last dose. Follow up visit #2 (FU2) occurs approximately 80 days (+/- 7 days) after FU1.
- b Survival visits = every 3 months (+/- 7 days) from FU2 until the end of the study (5 years from the primary analysis of DFS). FU2 visits may be conducted during clinic visit or via the telephone.
- c Laboratory toxicities (eg, suspected drug induced liver enzyme elevations) will be monitored during the follow-up phase via on site/local labs until all study drug related toxicities resolve, return to baseline, or are deemed irreversible.

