- Cystoscopy in subjects with upper GU primaries who still have bladder intact will occur in addition to other tumor imaging assessments every 12 weeks from the date of first dose to Week 48 (i.e. Week 12, 24, 36, 48 +/- 1 week), then every 24 weeks from Week 48 to Week 96 (i.e. Week 72, 96; +/- 2 weeks), then every 48 weeks until non-urothelial tract recurrence or treatment is discontinued (whichever occurs later) for a maximum of 5 years (i.e. Week 144, 192, 240; +/- 4 weeks).

█ [REDACTED]

█ [REDACTED]

- Subjects will have two follow-up visits (FU1 and FU2) for safety within approximately 100 days from the last dose of study therapy, according to Table 5.1-3. Beyond this time period, subjects will be followed for survival and ongoing drug related AEs until these events have resolved, returned to baseline or are deemed irreversible.
- After discontinuation of study therapy (nivolumab/placebo) and completion of follow-up visits FU1 and FU2, subjects will be followed every 3 months (+/- 7 days) for survival and second progression until death, lost to follow-up, withdrawal of study consent or end of study.

Assuming an average accrual rate of 16 subjects per month, the accrual will take approximately 40 months. The total duration of the study from start of randomization to final analysis of DFS is expected to be 53 months (40 months of accrual + 13 months of follow-up) (Table 8.1-1). Additional survival follow-up may continue for up to 5 years from the primary analysis of DFS. The study will end once survival follow-up has concluded.

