Subjects must be followed for at least 100 days after the last dose of study therapy. Follow-up visit #1 (FU1) occurs approximately 35 days (+/- 7 days) after last dose or coinciding with the date of discontinuation (+/- 7 days) if the date of discontinuation is greater than 35 days after the last dose. Follow up visit #2 (FU2) occurs approximately 80 days (+/- 7 days) after FU1. Survival visits are every 3 months from FU2 until the end of the study (5 years from the primary analysis of DFS) and may be conducted during a clinic visit or via the phone. The co-primary endpoint of this study is DFS in all randomized and in PD-L1 expressers ($\geq 1\%$ membranous tumor staining) and a key secondary endpoint is OS so tracking and reporting the subject's status in the follow up setting according to the protocol guidelines for disease recurrence and survival are critical to the final study analysis. The importance of follow up should be clearly communicated to study subjects.

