5.3 Safety Assessments

At baseline, a medical history will be obtained to capture relevant underlying conditions. The baseline examinations should include signs and symptoms, weight, height, ECOG Performance Status, BP, HR and temperature should be performed within 72 hours prior to first dose. Concomitant medications will also be collected from within 14 days prior to first dose and through the study treatment period (See [Table 5.1-1](#) and [Table 5.1-2](#)).

Baseline local laboratory assessments should be done within 14 days prior to the first dose and include: CBC w/differential, LFTs (ALT, AST, total bilirubin, alkaline phosphatase), BUN or serum urea level, creatinine, Ca, Mg, Na, K, Cl, LDH, glucose, and, if clinically indicated, urine cytology. Amylase, lipase, TSH, Free T4, Free T3, and Hep B and C testing (HBV sAg and HCV RNA or Ab) should be done within 28 days. Pregnancy testing for WOCBP (done locally) to be done within 24 hours prior to first dose, and then every 4 weeks (+ or – 1 week) regardless of dosing schedule, and at each safety follow up visit (Follow up visits 1 and 2). See [Table 5.1-1](#), [Table 5.1-2](#), and [Table 5.1-3](#).

On-study local laboratory assessments should be done within 72 hours prior to each dose through Week 23 visit and every alternative dose thereafter. Liver function tests (AST, ALT, ALP, T. Bili) will be analyzed within 72 hours prior to each dose throughout the treatment period. Labs should be reviewed by investigator prior to treatment. Subjects will be evaluated for safety if they have received any study drug. Adverse events (AE) assessments will be performed continuously during the treatment phase. During the safety follow-up phase ([Table 5.1-3](#)) AE assessments

should be done in person. Once subjects reach the survival follow-up phase, either in-person visits or documented telephone calls or emails to assess the subject's status are acceptable.

Adverse events and laboratory values will be graded according to the NCI-CTCAE version 4.0.

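### Footnote b of Table 5.1-3 gives the telephone option to FU2, an in-person safety visit, where survival visits were evidently meant

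*Protocol*

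**What the plan says.** Table 5.1-3 of the protocol sets out follow-up after study therapy in two columns: Follow Up Visits 1 and 2, which carries footnote a, and Survival Follow-Up Visits, which carries footnote b.

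- **Footnote a** times the safety visits. FU1 comes about 35 days (+/- 7) after the last dose, or at discontinuation if that is later. For FU2 it says "Follow up visit #2 (FU2) occurs approximately 80 days (+/- 7 days) after FU1".
- **Footnote b** first defines survival visits as three-monthly from FU2 to the end of the study. It then says "FU2 visits may be conducted during clinic visit or via the telephone".
- **Table rows.** In the Visits 1 and 2 column, X marks stand against the targeted physical examination, the adverse events assessment and the pregnancy test for women of childbearing potential. The note on the examination gives its purpose: "To assess for potential late emergent study drug related issues". The survival column is blank for all three. The Survival Status row, marked only in the survival column, allows phone contact or an office visit.
- **Section 3.1.1** states "Subjects will have two follow-up visits (FU1 and FU2) for safety within approximately 100 days from the last dose of study therapy". It places survival follow-up after both: "completion of follow-up visits FU1 and FU2, subjects will be followed every 3 months (+/- 7 days) for survival and second progression".
- **Section 3.5** describes the survival visits in nearly the same terms as footnote b, and there it is the survival visits that are three-monthly "and may be conducted during a clinic visit or via the phone".
- **Section 5.3** says that adverse event assessments in the safety follow-up phase, citing Table 5.1-3, "should be done in person. Once subjects reach the survival follow-up phase, either in-person visits or documented telephone calls or emails" are acceptable. It also requires pregnancy testing "and at each safety follow up visit (Follow up visits 1 and 2").

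**The concern.** The footnote attaches the telephone option to the wrong visit. FU2 is not a survival visit. It is the second of two safety visits, and survival follow-up starts only once it is complete. A cardiovascular, gastrointestinal and pulmonary examination cannot be done by telephone, so the table both requires an examination at FU2 and permits FU2 to take place without one.

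Sites run visits from the schedule table, and this is the only legible sentence in it about how FU2 is conducted. A coordinator who acts on it could miss three things: the last scheduled examination for late-emerging drug-related problems, the in-person adverse event assessment, and, for women of childbearing potential, the second post-treatment pregnancy test. The risk is to safety follow-up of individual subjects and to consistency between sites. Nothing in the DFS or OS analyses depends on it.

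**Working it through.** The plan has no figure to reproduce here. The check is a comparison of texts, followed by simple arithmetic on the visit windows.

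**1. Which visit gets the telephone option?**

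| Place in the protocol | Visit given the telephone option |
|---|---|
| Table 5.1-3, footnote b | FU2 |
| Table 5.1-3, Survival Status row | Survival visits |
| Section 3.5 | Survival visits |
| Section 5.3 | Contacts from the survival follow-up phase onward; in person before that |

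Footnote b stands alone against the other three.

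**2. Could FU2 in footnote b loosely mean visits from FU2 onward?** Footnote a, directly above, uses FU2 for follow-up visit 2 at a stated time, and Section 3.1.1 counts it as one of two safety visits. A reader of the table has no reason to give it a wider meaning.

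**3. Likely origin.** Section 3.5 says in one sentence that survival visits run every three months from FU2 and may be held in clinic or by phone. Footnote b has the same content in two sentences, and the subject of the second has become FU2.

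**4. Is this an effect of redaction or text extraction?** No. The column markers, the three X-marked rows and both footnotes are legible. Redacted rows prevent a full list of FU2 procedures but do not affect the conflict.

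**5. Schedule interval at stake if the FU2 examination is not done.**

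- Inputs: FU1 at 35 +/- 7 days after last dose, so day 28 to 42; FU2 at FU1 + 80 +/- 7 days (Section 3.5 and footnote a).
- By footnote a, the last examination moves earlier by 80 - 7 = 73 to 80 + 7 = 87 days. FU2 itself falls between day 28 + 73 = 101 and day 42 + 87 = 129, nominally 35 + 80 = day 115.
- Section 3.1.1 instead puts both visits within about 100 days of last dose. With FU2 held at day 100, the shift is 100 - 42 = 58 to 100 - 28 = 72 days, nominally 100 - 35 = 65. It is less if FU2 is earlier.
- If FU1 is later because discontinuation came more than 35 days after the last dose, the first range is unchanged and the second shrinks.

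**The case against.** The strongest reply is that the protocol already resolves the point. Footnote b is attached only to the survival column, so a site planning FU2 is sent to footnote a, which offers no telephone option. Section 5.3 is explicit about in-person assessment and about pregnancy testing at both safety visits. Footnote b concerns the mode of contact and waives no procedure, so the X marks still bind. That all stands: a careful site would examine the subject at FU2, and the harm is conditional on a literal reading.

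A second reply is that the survival column also contains tumor imaging, which cannot be done by telephone either. If the option is harmless there, it should be harmless at FU2. This does not carry over. Imaging follows its own calendar from the first dose, whereas the examination belongs to FU1 and FU2 themselves. Section 3.5 already gives survival visits the telephone option, so the correction adds nothing new to that column.

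Third, other safeguards limit the consequence. Serious and nonserious adverse events are collected to 100 days after dosing (Sections 6.1.1 and 6.2.1), laboratory toxicities are followed under footnote c, and ongoing drug-related events are followed to resolution, return to baseline or irreversibility (Section 3.1.1). This is correct, though none of it replaces an examination meant to find problems not yet reported.

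Finally, the day counts restate the schedule and do not measure harm. That is accepted. The difference between Section 3.1.1 and footnote a on when FU2 falls is a separate matter, which this correction leaves as it is.

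**Conclusion.** The inconsistency is real and footnote b is wrong as written. Confidence in that is high, because it rests on legible current text. Confidence that any subject would be harmed is a different matter: the documents do not give the number of sites that would read the footnote literally, or the number of subjects or women of childbearing potential affected.

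One of the two scheduled post-treatment safety examinations is exposed. The interval in the previous calculation assumes that FU1 takes place on schedule and that the FU2 examination is actually omitted. Clear text elsewhere makes the intended meaning certain, which lowers the risk but does not correct the rule in the visit schedule. This is a low-priority correction, worth making because it changes what sites are told they may do.

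**What to change.** In the last sentence of footnote b to Table 5.1-3, replace the words FU2 visits with Survival visits and leave the rest of the sentence alone. The footnote then agrees with Section 3.5, Section 5.3 and the Survival Status row.

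Made at the next protocol amendment, this costs almost nothing. If the sponsor wants sites told sooner, an administrative letter would serve, but under Section 9.1.1 investigators must then inform their IRB/IEC, a small task at every site. No visit, procedure or analysis is added or changed.
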